**Appendix IV**

**CRADA/CTA**

The agent(s) supplied by CTEP, DCTD, NCI used in this protocol is/are provided to the NCI under a Collaborative Agreement (CRADA, CTA, CSA) between the Pharmaceutical Company(ies) (hereinafter referred to as "Collaborator(s)") and the NCI Division of Cancer Treatment and Diagnosis. Therefore, the following obligations/guidelines, in addition to the provisions in the "Intellectual Property Option to Collaborator" ([http://ctep.cancer.gov/industryCollaborations2/intellectual\\_property.htm](http://ctep.cancer.gov/industryCollaborations2/intellectual_property.htm)) contained within the terms of award, apply to the use of the Agent(s) in this study:

1. Agent(s) may not be used for any purpose outside the scope of this protocol, nor can Agent(s) be transferred or licensed to any party not participating in the clinical study. Collaborator(s) data for Agent(s) are confidential and proprietary to Collaborator(s) and shall be maintained as such by the investigators. The protocol documents for studies utilizing Agents contain confidential information and should not be shared or distributed without the permission of the NCI. If a copy of this protocol is requested by a patient or patient's family member participating on the study, the individual should sign a confidentiality agreement. A suitable model agreement can be downloaded from: <http://ctep.cancer.gov>.
2. For a clinical protocol where there is an investigational Agent used in combination with (an) other Agent(s), each the subject of different Collaborative Agreements, the access to and use of data by each Collaborator shall be as follows (data pertaining to such combination use shall hereinafter be referred to as "Multi-Party Data"):
  - a. NCI will provide all Collaborators with prior written notice regarding the existence and nature of any agreements governing their collaboration with NCI, the design of the proposed combination protocol, and the existence of any obligations that would tend to restrict NCI's participation in the proposed combination protocol.
  - b. Each Collaborator shall agree to permit use of the Multi-Party Data from the clinical trial by any other Collaborator solely to the extent necessary to allow said other Collaborator to develop, obtain regulatory approval or commercialize its own Agent.
  - c. Any Collaborator having the right to use the Multi-Party Data from these trials must agree in writing prior to the commencement of the trials that it will use the Multi-Party Data solely for development, regulatory approval, and commercialization of its own Agent.
3. Clinical Trial Data and Results and Raw Data developed under a Collaborative Agreement will be made available to Collaborator(s), the NCI, and the FDA, as appropriate and unless additional disclosure is required by law or court order as described in the IP Option to Collaborator ([http://ctep.cancer.gov/industryCollaborations2/intellectual\\_property.htm](http://ctep.cancer.gov/industryCollaborations2/intellectual_property.htm)). Additionally, all Clinical Data and Results and Raw Data will be collected, used and disclosed consistent with all applicable federal statutes and regulations for the protection of human subjects, including, if applicable, the *Standards for Privacy of Individually Identifiable Health Information* set forth in 45 C.F.R. Part 164.
4. When a Collaborator wishes to initiate a data request, the request should first be sent to the NCI, who will then notify the appropriate investigators (Group Chair for Cooperative Group studies, or PI for other studies) of Collaborator's wish to contact them.

5. Any data provided to Collaborator(s) for Phase 3 studies must be in accordance with the guidelines and policies of the responsible Data Monitoring Committee (DMC), if there is a DMC for this clinical trial.
6. Any manuscripts reporting the results of this clinical trial must be provided to CTEP by the Group office for Cooperative Group studies or by the principal investigator for non-Cooperative Group studies for immediate delivery to Collaborator(s) for advisory review and comment prior to submission for publication. Collaborator(s) will have 30 days from the date of receipt for review. Collaborator shall have the right to request that publication be delayed for up to an additional 30 days in order to ensure that Collaborator's confidential and proprietary data, in addition to Collaborator(s)'s intellectual property rights, are protected. Copies of abstracts must be provided to CTEP for forwarding to Collaborator(s) for courtesy review as soon as possible and preferably at least three (3) days prior to submission, but in any case, prior to presentation at the meeting or publication in the proceedings. Press releases and other media presentations must also be forwarded to CTEP prior to release. Copies of any manuscript, abstract and/or press release/ media presentation should be sent to:

Email: [[contact]](mailto:[contact])

The Regulatory Affairs Branch will then distribute them to Collaborator(s). No publication, manuscript or other form of public disclosure shall contain any of Collaborator's confidential/proprietary information.

---

**A Randomized Phase III Trial of Endocrine Therapy plus Entinostat/Placebo in Patients  
with Hormone Receptor-Positive Advanced Breast Cancer**

**Appendix V**

**ECOG Performance Status**

PS 0	Fully active, able to carry on all pre-disease performance without restriction
PS 1	Restricted in physically strenuous activity but ambulatory and able to carry out work of a light or sedentary nature e.g., light house work, office work.
PS 2	Ambulatory and capable of all self-care but unable to carry out any work activities. Up and about more than 50% of waking hours.
PS 3	Capable of only limited self-care, confined to bed or chair more than 50% of waking hours.
PS 4	Completely disabled. Cannot carry on any self-care. Totally confined to bed or chair.

---

**A Randomized Phase III Trial of Endocrine Therapy plus Entinostat/Placebo in Patients with Hormone Receptor-Positive Advanced Breast Cancer**

Rev.10/16

Rev. 9/17

**Appendix VI**

**E2112 Collection and Shipping Kit Order Instructions**

As of February 12, 2016 Specimen Collection/Shipping Kits are provided by CENETRON CENTRAL LABORATORIES and are to be ordered ONLINE.

Starter kits are not available. Kit requests are to be made AFTER patient randomization.

Questions regarding kits can be directed to [[contact]](mailto:[contact]) or call the Cenetron Clinical Trials Group at [contact].

Ordering process:

- At time of patient randomization, provide the contact for kit ordering in OPEN
- Following randomization of the patient to the trial, Go to the website [www.cenetron.com](http://www.cenetron.com) and Click on the “Order Kits” button at the top right. It is recommended that kits be ordered same day as patient randomization.
- The Order Form is not study specific and can be used for any study. Complete the online form as follows
  - **Sponsor (REQUIRED):** ECOG-ACRIN
  - **Contact Name (REQUIRED):** Name of the site’s kit contact. Should match the name of the individual provided in OPEN as the kit contact
  - **Protocol Number (REQUIRED):** E2112
  - **Phone Number (REQUIRED):** Phone number of the kit contact. Please insure that this is a number that can be reached from an external caller.
  - **FAX Number:** Fax number of the kit contact
  - **Investigator:** Last name of the kit contact is adequate
  - **Email (REQUIRED):** The email of the site’s kit contact. Must be entered twice to confirm
  - **Date Supplies Needed (REQUIRED):** Add 3 business days or more to order date. E.g. if ordering on 2/5/2016, indicate 2/10/2016 to accommodate the weekend. Reminder that holidays must also be considered in this timeline.
  - **KIT NAME (required):** E2112 Collection Kit
  - **Quantity:** 1
  - **Comments:** Provide E2112 Case ID and full shipping address
    - “Patient case ID =” #####
    - Ship kit to Name of the individual to whom the kit is shipped. May be different than the kit contact provided above.
    - Full street address, town, state and zip code
  - Answer the security question

Please complete this form correctly, including the valid ECOG-ACRIN case number and complete shipping address. If information is missing kit processing will be delayed.

**A Randomized Phase III Trial of Endocrine Therapy plus Entinostat/Placebo in Patients with Hormone Receptor-Positive Advanced Breast Cancer**

**Appendix VII**

**E2112 Mandatory Participating Site Training Form**

Protocol Number	E2112
Protocol Name	A Randomized Phase III Trial of Endocrine Therapy Plus Entinostat/Placebo in Patients with Hormone Receptor-Positive Advanced Breast Cancer

Instructions for Mandatory Participating Site Training Course:

- Each site participating in E2112 is required to have at least **one person** (i.e. research coordinator or investigator, etc) from the research staff complete ECOG-ACRIN's E2112 mandatory participating site training course.
- This course must be completed **PRIOR to the first patient enrollment** for the site.
- **An ENROLLMENT BLOCK** is in place within the OPEN system which will prevent the site from enrolling patients until this training requirement is complete.
- Please note that ECOG-ACRIN recommends **all research staff** (CRAs, Data Managers, Imaging Staff, Investigators, Pharmacy Staff, etc) involved in E2112 complete the training course.

The training course is available 24/7 via the following URL:

<http://coccg.mindflash.com/PublicCoursePage.aspx?c=832897692>

Please complete the bottom of this form and submit it directly to the CTSU Regulatory Office via [contact] or Email: [[contact]](mailto:[contact]).

**Section A:** Please provide the name of one of the individuals who completed the E2112 mandatory participating site training course.

Name	CTEP ID (Associate or Investigator)

**Section B:** Please provide **ALL Site Name(s)** and **Site CTEP IDs** where the research staff that completed this course may enroll a patient to E2112:

Site Name	Site CTEP ID (example: AL000)

**Section C:** Please complete.

\_\_\_\_\_

Name

\_\_\_\_\_

Signature

\_\_\_\_\_

Date

**Thank you for your participation.**

---

**A Randomized Phase III Trial of Endocrine Therapy plus Entinostat/Placebo in Patients with Hormone Receptor-Positive Advanced Breast Cancer**

Rev.10/15  
Rev. Add5

**Appendix VIII**

**Instructions for Reporting Pregnancies on a Clinical Trial**

**What needs to be reported?**

Rev.10/16

All pregnancies and suspected pregnancies (including a positive or inconclusive pregnancy test regardless of age or disease state) of a female patient while she is on Entinostat/Placebo, or within 3 months of the patient's last dose of Entinostat/Placebo must be reported in an expeditious manner. The outcome of the pregnancy and neonatal status must also be reported.

**How should the pregnancy be reported?**

The pregnancy, suspected pregnancy, or positive/inconclusive pregnancy test must be reported via CTEP's Adverse Event Reporting System (CTEP-AERs)

([http://ctep.cancer.gov/protocolDevelopment/electronic\\_applications/adverse\\_events.htm](http://ctep.cancer.gov/protocolDevelopment/electronic_applications/adverse_events.htm))

**When does a pregnancy, suspected pregnancy or positive/inconclusive pregnancy test need to be reported?**

An initial report must be done within 24 hours of the Investigator's learning of the event, followed by a complete expedited CTEP-AERs report within 5 calendar days of the initial 24-hour report.

**What other information do I need in order to complete the CTEP-AERs report for a pregnancy?**

- The pregnancy (fetal exposure) must be reported as a Grade 3 "Pregnancy, puerperium and perinatal conditions – Other (pregnancy)" under the System Organ Class (SOC) "Pregnancy, puerperium and perinatal conditions"
- The pregnancy must be reported within the timeframe specified in the Adverse Event Reporting section of the protocol for a grade 3 event.
- The start date of the pregnancy should be reported as the calculated date of conception.
- The potential risk of exposure of the fetus to the investigational agent(s) or chemotherapy agent(s) should be documented in the "Description of Event" section of the CTEP-AERs report.

**What else do I need to know when a pregnancy occurs to a patient?**

- The Investigator must follow the female patient until completion of the pregnancy and must report the outcome of the pregnancy and neonatal status via CTEP-AERs.
- The decision on whether an individual female patient can continue protocol treatment will be made by the site physician in collaboration with the study chair and ECOG-ACRIN Operations Office – Boston. Please contact the ECOG-ACRIN Operations Office – Boston to ask for a conference call to be set up with the appropriate individuals.
- *It is recommended the female subject be referred to an obstetrician-gynecologist, preferably one experienced in reproductive toxicity for further evaluation and counseling.*

### **How should the outcome of a pregnancy be reported?**

The outcome of a pregnancy should be reported as an *amendment* to the initial CTEP-AERs report if the outcome occurs on the same cycle of treatment as the pregnancy itself. However, if the outcome of the pregnancy occurred on a subsequent cycle, a *new* CTEP-AERs report should be initiated reporting the outcome of the pregnancy.

### **What constitutes an abnormal outcome?**

An abnormal outcome is defined as any pregnancy that results in the birth of a child with persistent or significant incapacity or substantial disruption of the ability to conduct normal life functions (formerly referred to as disabilities), congenital anomalies, or birth defects. For assistance in recording the grade or category of these events, please contact the CTEP AEMD Help Desk at [contact] or [[contact]](mailto:[contact]), for it will need to be discussed on a case by case basis.

### **Reporting a Pregnancy Loss**

A pregnancy loss is defined in CTCAE as “*A death in utero.*”

It must be reported via CTEP-AERs as Grade 4 “*Pregnancy loss*” under the System Organ Class (SOC) “*Pregnancy, puerperium and perinatal conditions*”.

A fetal death should **NOT** be reported as a Grade 5 event as currently CTEP-AERs recognizes this event as a patient’s death.

### **Reporting a Neonatal Death**

A neonatal death is defined in CTCAE as “*A disorder characterized by cessation of life occurring during the first 28 days after birth*” that is felt by the investigator to be at least possibly due to the investigational agent/intervention. However, for this protocol, any neonatal death that occurs within 28 days of birth, without regard to causality, must be reported via CTEP-AERs AND any infant death after 28 days that is suspected of being related to the *in utero* exposure to Entinostat/Placebo must also be reported via CTEP-AERs.

It must be reported via CTEP-AERs as Grade 4 “*Death neonatal*” under the System Organ Class (SOC) “*General disorder and administration site conditions*”.

A neonatal death should **NOT** be reported as a Grade 5 event as currently CTEP-AERs recognizes this event as a patient’s death.

### **Additional Required Forms:**

When submitting CTEP-AERs reports for pregnancy, pregnancy loss, or neonatal loss, the **CTEP ‘Pregnancy Information Form’** must be completed and faxed along with any additional medical information to CTEP [contact]). This form is available on CTEP’s website

([http://ctep.cancer.gov/protocolDevelopment/electronic\\_applications/docs/PregnancyReportForm.pdf](http://ctep.cancer.gov/protocolDevelopment/electronic_applications/docs/PregnancyReportForm.pdf))

**A Randomized Phase III Trial of Endocrine Therapy plus Entinostat/Placebo in Patients with Hormone Receptor-Positive Advanced Breast Cancer**

Rev.10/16

**Appendix IX**

**E2112 Covance Site Information/Initial Kit Order Form**

**\*\*\*If your site is not participating in the optional population PK study, this form is not required\*\*\***

Please complete this form for the initial shipment of three (3) kits and the Site Laboratory Instruction Manual. Covance requires ten (10) days to process this form and ship out the initial kits. Please complete and Email this form to Syndax ([[contact]](mailto:[contact])) or Fax to [contact], Attn: [name]) as soon as possible.

Once two of the three initial kits are received by Covance an auto-resupply of one kit will be sent out by Covance. If more kits are needed than provided by the auto-resupply, please contact Covance directly at the number provided in the Site Laboratory Instruction Manual. Shipment usually takes about five (5) to seven (7) business days.

Attn: Clinical Trials Manager

Date:

NCI CTEP ID#:

Please write using block letters

**Appendix X**

**Sarcopenia Imaging Substudy**

**Impact of muscle quality and quantity on outcome in patients receiving endocrine based therapy for metastatic breast cancer in ECOG- 2112**

Investigator: [name]., Indiana University

Statistician: [name], Brown University

**Background**

Observational data investigating the relationship between body habitus and outcome or toxicity in breast cancer has been largely centered on weight-based metrics such as BMI, with variable and inconsistent results. Body weight alone does not tell a full story, as body composition is highly variable with respect to muscle and adipose tissue. Muscle is a large, active endocrine organ affecting physical function, quality of life, metabolism, and inflammation, and may impact outcome or toxicity in metastatic breast cancer (MBC) patients receiving endocrine based therapies.

Rev. Add7

Low muscle mass (LMM) has been associated with poorer outcome and increased toxicity in advanced cancer. Low muscle attenuation (LMA), reflecting muscle “quality” and intramuscular fat infiltration, is also associated with poor outcome. In comparison to muscle mass, muscle attenuation correlates better with muscle strength and function. The few studies that have investigated these parameters in patients with MBC have been small and focused on patients receiving cytotoxic chemotherapy. The largest of these was a retrospective study of patients receiving first line chemotherapy, finding no significant difference in overall survival based on LMM (40 versus 30 months,  $p=0.07$ ), but a significantly reduced survival for those patients with LMA (23 versus 15 months,  $p = 0.005$ ).

To date, there has been no evaluation of how muscle characteristics affect outcome or toxicity in patients receiving endocrine therapy for MBC. The ongoing study E2112, a randomized, double-blinded phase III study of exemestane with or without the HDAC inhibitor entinostat with co-primary objectives of progression free survival (PFS) and/or overall survival (OS), offers a homogeneous population with centrally collected imaging and outcome follow-up to investigate this question.

**Specific hypotheses:**

1. Primary: Low muscle attenuation (LMA) is prognostic of poor overall survival in patients receiving endocrine based therapy for metastatic breast cancer (MBC)
2. Secondary: Low muscle mass (LMM) is prognostic of poor overall survival in patients receiving endocrine based therapy for MBC.

**Objectives:**

1. Primary: To determine the prognostic value of baseline LMA by CT imaging on overall survival in patients receiving endocrine based therapy for MBC.
2. Secondary:
  - To determine the prognostic value of baseline LMM by CT imaging on overall survival in patients receiving endocrine based therapy for MBC.

- To determine the prognostic value of LMA and LMM on overall survival in the subset of patients receiving endocrine based therapy for metastatic breast cancer who have sarcopenic obesity at study entry.
- To assess the correlation between LMA, LMM, and sarcopenic obesity with PRO\_CTCAE of muscle ache and joint pain at 3 months.
- To assess the correlation between LMA, LMM, and sarcopenic obesity with patient reported health related quality of life score at 3 months.
- To determine the optimal stratification for LMA and LMM to predict overall survival.

### **Study Design:**

In this proposed imaging correlative study, evaluation of muscle attenuation and mass will be determined using baseline CT scans collected for central review. A transverse cut at the L3 level will be extracted, as muscle area at this level is linearly related to whole body muscle mass. SliceOmatic software (version 5, Tomovision) will be used to process images, providing a highly accurate estimation of cross-sectional skeletal muscle area and muscle attenuation with high inter-observer reliability. The software is semi-automated and will be run by two independent investigators, with a subset of images read by both investigators to determine a coefficient of variation. LMM is defined as skeletal muscle index (SMI, lean muscle area/height, cm^2/m^2) less than 41 and LMA will be defined as average muscle density less than 25 HU, or less than 33 HU if the patient is overweight/obese by BMI. These cut-points are based on previously determined thresholds associated with reduced survival in patients with metastatic solid tumors. An additional exploratory objective will be to determine whether there are alternate cut-points predictive of survival in this particular population based on optimal stratification.

This evaluation will allow us to establish prevalence of LMM and LMA in this population, and to investigate the importance of muscle mass and quality, rather than body weight alone, on outcomes and toxicity in patients receiving AI-based therapy for MBC. This may lead to further refinement of prognostic/stratification criteria, support development of targeted exercise interventions, and investigation of AI drug resistance or alternate dosing strategies. In addition, the use of CT software to quickly calculate body composition measures may have important clinical applications across many treatments and disease types within ECOG-ACRN trials.

### **Statistical Design and Analysis:**

#### Primary Endpoint:

- Overall Survival (OS) defined as time from start of on-study therapy to death from any cause.

#### Sample size and power justification:

We will plan initially to evaluate the study population as a whole (n=600), and later analyze the treatment and placebo groups separately (n=300 per group) once primary data are available. For the primary objective, assuming 60% of participants have LMA, we will have a 95% power to detect a difference in median survival time between 20 and 28 months (HR 1.4) for those with LMA versus those without LMA, based on a two- sided log rank test with type I error rate of 0.05. Reducing the sample size to 300 participants, we will achieve a 73% power to detect the same difference in median survival time.

Study population	% LMA	Median survival for LMA (month)	Median survival for non-LMA (month)	Hazard ratio	Study power(%)
600	60%	20	28	1.4	95
300	60%	20	28	1.4	73

Statistical analysis plan:

1. Primary aim:

- To determine the prognostic value of LMA on overall survival in patients receiving endocrine based therapy for metastatic breast cancer.
  - Kaplan Meier survival curve and log-rank test are used to test the difference in OS between the LMA participants and the non-LMA participants. Multivariable Cox proportional hazard model will be used to model the association between LMA and OS while adjusting for age, race, prior chemotherapy, ECOG PS and BMI.

2. Secondary aims:

- To determine the prognostic value of LMM on overall survival in patients receiving endocrine based therapy for metastatic breast cancer.
  - Kaplan Meier survival curve and log-rank test are used to test the difference in OS between the LMM participants and the non-LMM participants.
- To determine the prognostic value of LMA and LMM on overall survival in the subset of patients receiving endocrine based therapy for metastatic breast cancer who have sarcopenic obesity at study entry.
  - Kaplan Meier survival curve and log-rank test are used to test the difference in OS between the sarcopenic obese participants who had LMA or LMM and those without LMA or LMM.
- To assess correlation between LMA, LMM, and sarcopenic obesity with PRO\_CTCAE of muscle ache and joint pain at 3 months  
We will use two sample t-test to compare the muscle ache score or joint pain score between participants who had LMA (or LMM, or sarcopenic obesity) with those who didn't.
- To assess the correlation between LMA, LMM, and sarcopenic obesity with patient reported health related quality of life score at 3 months.  
We will use two sample t-test to compare the quality of life score between participants who had LMA (or LMM, or sarcopenic obesity) with those who didn't.
- To determine the optimal stratification for LMA and LMM to predict overall survival.
  - We will use a search algorithm, together with the method of the time-dependent ROC curve to determine the optimal cut-off point for the determination of LMA and LMM to identify groups with differential overall survival.

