### 9.2 Study Design

Patients with histologic confirmation of invasive adenocarcinoma of the breast will be randomized according to the permuted block algorithm with a 1:1 randomization ratio to arms A and B. Stratification factors include:

- Setting in which patient developed resistance to prior non steroidal AI treatment (adjuvant vs. metastatic)
- Geographic region (USA vs. other)
- Visceral disease (yes vs. no)
- Prior fulvestrant use (yes vs. no)

**NOTE:** Visceral disease is defined as lung and/or liver involvement.

Taking into consideration the accrual rates of the BOLERO-2 study (40 patients/month, 700 patients over 18 months with 24 international sites), the ENCORE 301 study (5 patients/month, 130 patients over 2 years at 38 sites US and international) and the CONFIRM study (24 patients/month at 128 sites), all of which have been conducted in the AI refractory setting, and the 1st line SWOG

S0226 study (10 patients/month, 700 patients over 6 years), we anticipate an accrual rate of approximately 15 patients per month in our study.

Enrollment of 600 patients will be required to provide adequate power for the OS endpoint (see Section [9.2.2](#)). The first 360 patients will be used for the primary evaluation of PFS (see Section [9.2.1](#)), objective response rate (ORR), toxicity, time to treatment deterioration and patient-reported outcomes. If the PFS analysis is positive, the data for first 360 patients would be used for a submission to the FDA. At the time of final analysis for the OS endpoint, secondary analyses of PFS, objective response and toxicity will be conducted in all 600 patients, along with the primary analyses for the pharmacodynamic acetylation marker data and adherence to protocol therapy data. Imaging studies for all 600 participants will be collected and archived at the ACR Imaging Core Laboratory.

For purposes of comparability to the phase 3 study of exemestane in advanced breast cancer patients by Chia et al., enrollment in this study will attempt to achieve a target patient population that consists of approximately 80% of patients having measurable disease (with at least 1 measurable lesion at baseline assessment and identification of up to 5 total target lesions [maximum of 2 lesions per organ] and 5 total non-target lesions) and approximately 20% of patients having non-measurable disease only.

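### Appendix X tests muscle attenuation against survival without any measure of disease extent, although visceral disease is recorded for every patient at randomization

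*Combined protocol and SAP*

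**What the plan says.** Appendix X, statistical analysis plan, primary aim, gives the test: "Kaplan Meier survival curve and log-rank test are used to test the difference in OS between the LMA participants and the non-LMA participants". No stratification is mentioned. A multivariable Cox model follows, "adjusting for age, race, prior chemotherapy, ECOG PS and BMI".

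The power statement in Appendix X rests on a two-sided "log rank test with type I error rate of 0.05", "assuming 60% of participants have LMA", with medians of 20 and 28 months (hazard ratio 1.4). It gives 95% power at 600 patients and 73% at 300. The study population is analysed as a whole first, and each arm separately once the primary data are available. The Study Design paragraph names, as one possible use of the results, sharpening the criteria by which patients are classified prognostically or stratified.

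Sections 4.3 and 9.2 list four stratification factors: setting of resistance to the non-steroidal aromatase inhibitor, region, prior fulvestrant, and "Visceral disease (yes vs. no"), defined as liver and/or lung involvement. Sections 9.2.2 and 9.4 stratify the main survival test on these factors. The multivariable models in Section 9.4 also allow for stage at diagnosis and prior hormonal therapy.

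**The concern.** The main trial compares randomized arms, so confounding by baseline disease is not its problem, yet it stratifies on visceral disease. Appendix X compares groups defined by a patient characteristic, where confounding is possible, and uses neither visceral disease nor any other direct measure of disease extent. ECOG performance status is at best a partial proxy, and eligibility restricts it to 0-1.

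Two things are at stake. First, if patients with liver or lung involvement tend to have poorer muscle, LMA will look prognostic partly because it marks more extensive disease. Second, showing that LMA could refine existing stratification criteria requires showing that it carries information beyond them. A model that leaves those factors out cannot do so, whatever the size of any confounding.

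**Working it through.** **1. The plan's own power figures.** For a two-group log-rank test with d deaths and LMA share p, power = Φ(|ln HR| × √(d·p(1−p)) − 1.96). Here p(1−p) = 0.6 × 0.4 = 0.24 and ln 1.4 = 0.3365.

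- Deaths needed for 95%: (1.960 + 1.645)² / (0.24 × 0.3365²) ≈ 479. For 73%: (1.960 + 0.613)² / (0.24 × 0.3365²) ≈ 244.
- Appendix X states neither deaths nor follow-up. With exponential survival, uniform accrual over 40 months (Section 9.2.2) and an assumed 36 months of further follow-up, 600 patients yield about 482 deaths and 95.1% power. With 300 patients power is 72.5%. The stated figures therefore reproduce under that assumption.
- At the 410 deaths planned for the main survival analysis, power is 91.6%. At half that number it is 65.5%.

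The power figures are not in dispute here. They show that the powered test is the two-group log-rank test, not the Cox model.

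**2. Crude confounding by visceral disease.** Suppose LMA has no effect, visceral disease multiplies the hazard of death by h, and its prevalence is p₁ with LMA and p₀ without. Then approximately

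apparent HR = [1 + p₁(h − 1)] / [1 + p₀(h − 1)].

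At 410 deaths √(410 × 0.24) = 9.92, so z = 9.92 × ln(apparent HR). The chance of two-sided significance is Φ(z − 1.96) + Φ(−z − 1.96). The documents give none of p₁, p₀ and h; all three are assumptions.

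| p₁ vs p₀ | h | Apparent HR | ln HR | Share of ln 1.4 | z | Declared significant |
|---|---|---|---|---|---|---|
| 60% vs 50% | 1.5 | 1.30/1.25 = 1.04 | 0.039 | 12% | 0.39 | 7% |
| 60% vs 50% | 2.0 | 1.60/1.50 = 1.07 | 0.065 | 19% | 0.64 | 10% |
| 70% vs 55% | 2.0 | 1.70/1.55 = 1.10 | 0.092 | 27% | 0.92 | 15% |

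For scale, the smallest LMA hazard ratio that reaches p < 0.05 at 410 deaths is exp(1.96/9.92) = 1.22. None of these scenarios reaches it by bias alone; they raise the chance that sampling error does the rest.

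**3. Check by simulation.** There were 2,000 trials per scenario, each with 600 patients, 60% LMA, 40 months of accrual, analysis at 64 months, a treatment hazard ratio of 0.75 and about 430 deaths.

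- No LMA effect, 60% vs 50%, h = 1.5: LMA alone gives HR 1.040, significant in 6.9%. Adding visceral disease gives 1.000 and 5.2%.
- No LMA effect, 60% vs 50%, h = 2.0: 1.072 and 10.9%. Adding visceral disease gives 1.002 and 5.0%.
- A deliberately extreme case, 70% vs 40%, h = 2.0: 1.225 and 52.4%. Adding visceral disease gives 1.001 and 5.9%.
- Adding treatment arm alone changes nothing: 1.040 against 1.040, and 1.225 against 1.227.
- With a true LMA hazard ratio of 1.4, the model with visceral disease and arm keeps about 90% to 92% power.

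**4. Limit of these figures.** Steps 2 and 3 describe crude confounding. In the planned Cox model only the visceral imbalance that remains within levels of performance status and the other covariates matters. That is probably smaller, and the documents do not allow it to be estimated.

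**The case against.** The strongest reply is that Appendix X asks whether LMA is prognostic, not whether it is independently prognostic or causal. A marker that partly reflects disease extent can still be prognostic, and an unadjusted log-rank test answers that question correctly. This stands as far as it goes: the unadjusted test is not an error. It does not dispose of the point, because the plan itself adds an adjusted model and names a use that requires information beyond the existing stratification factors.

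It is also fair to say that no link between LMA and visceral disease is documented, and that stratification factors chosen for a randomized comparison are not thereby confounders of a muscle marker. The acetylation analysis in Section 9.5.2 also states no stratification for its log-rank test, although its Cox model includes disease stage and prior therapy. These arguments limit the size of the concern. They do not explain why an available measure of disease extent should be left out.

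A reader might infer that omitting treatment arm also makes LMA look prognostic. The documents do not support this: arm is randomized, LMA is read from baseline CT, and separate analyses by arm are already planned. Nor are the other three randomization factors measures of disease burden. Region is not one, and resistance setting and prior fulvestrant mainly describe treatment history. Visceral disease carries the argument.

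**Conclusion.** The point holds in a limited form. The Appendix X analysis includes no measure of disease extent although one is recorded for every patient, and as written it cannot show that LMA adds to the trial's own stratification factors. That second limitation needs no numerical assumption.

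The size of any bias is unknown. Under the assumed crude imbalances it is a spurious hazard ratio of 1.04 to 1.10 and a false-positive rate of about 7% to 15% at 410 deaths, probably lower after the planned covariates. Larger figures, such as the extreme simulated case, need an imbalance for which the documents give no evidence.

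It would go too far to conclude that LMA is only a stand-in for disease burden. It would also go too far to treat the adjusted Cox hazard ratio as the substudy's main result, since the powered test is the log-rank and a change to the Cox model alone would leave that test as it is. The main trial's conclusions are not affected. This is a free improvement of low severity.

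**What to change.** In Appendix X, primary aim:

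- Keep the unadjusted log-rank test, if wanted, as the description of crude prognostic value.
- Add a log-rank test stratified by the randomization factors.
- Add visceral disease and the other randomization factors to the multivariable Cox model.
- State that any claim of independent prognostic value rests on the stratified and adjusted results.
- Optionally include treatment arm once unblinded, for precision only.

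The cost is two or three sentences and no new data, since the factors are already collected. In the simulations, adjusting for visceral disease and arm left power at about 90% to 92% for a true hazard ratio of 1.4. The change should be made before survival is analysed by muscle attenuation, so that the covariates are not chosen after seeing the result. The same edit could state the number of deaths and the follow-up behind the 95% and 73% power figures.
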